Table 81: Summary Statistics for VT-11134 PK Parameters in Plasma, 40 mg Fasted Dose Group

This table will repeat Table 74 for VT-11134 PK parameters in plasma for the 40 mg Fasted Dose Group

Table 82: Summary Statistics for VT-11134 PK Parameters in Plasma, 80 mg Fasted Dose Group

This table will repeat Table 74 for VT-11134 PK parameters in Plasma for the 80 mg Fasted Dose Group

Table 83: Summary Statistics for VT-11134 PK Parameters in Plasma, 160 mg Fasted Dose Group

This table will repeat Table 74 for VT-11134 PK parameters in Plasma for the 160 mg Fasted Dose Group

Table 84: Summary Statistics for VT-11134 PK Parameters in Plasma, 160 mg Fed Dose Group

This table will repeat Table 74 for VT-11134 PK parameters in Plasma for the 160 mg Fed Dose Group

Table 85: Summary Statistics for VT-11134 PK Parameters in Plasma, 320 mg Fasted Dose Group

This table will repeat Table 74 for VT-11134 PK parameters in Plasma for the 320 mg Fasted Dose Group

Table 86: Summary Statistics for VT-11134 PK Parameters in Plasma, 640 mg Fasted Dose Group

This table will repeat Table 74 for VT-11134 PK parameters in Plasma for the 640 mg Fasted Dose Group

Table 87: Summary Statistics for VT-1598 PK Parameters in Urine by Dose Group

	40 mg Fasted	80 mg Fasted	160 mg Fasted	160 mg Fed	320 mg Fasted	640 mg Fasted
Inpatient Period (0-72 h)^a						
Ae _{last} (mg)	x (xx, xx)	x (xx, xx)	x (xx, xx)	x (xx, xx)	x (xx, xx)	x (xx, xx)
Ae%Dose (%)	x (xx, xx)	x (xx, xx)	x (xx, xx)	x (xx, xx)	x (xx, xx)	x (xx, xx)
CL _R (mL/min)	x (x)	x (x)	x (x)	x (x)	x (x)	x (x)
Nominal Collection Time Interval^a						
Ae ₀₋₆ (mg)	x (xx, xx)	x (xx, xx)	x (xx, xx)	x (xx, xx)	x (xx, xx)	x (xx, xx)
Ae ₆₋₁₂ (mg)	x (xx, xx)	x (xx, xx)	x (xx, xx)	x (xx, xx)	x (xx, xx)	x (xx, xx)
Ae ₁₂₋₂₄ (mg)	x (xx, xx)	x (xx, xx)	x (xx, xx)	x (xx, xx)	x (xx, xx)	x (xx, xx)
Ae ₂₄₋₃₆ (mg)	x (xx, xx)	x (xx, xx)	x (xx, xx)	x (xx, xx)	x (xx, xx)	x (xx, xx)
Ae ₃₆₋₄₈ (mg)	x (xx, xx)	x (xx, xx)	x (xx, xx)	x (xx, xx)	x (xx, xx)	x (xx, xx)
Ae ₄₈₋₆₀ (mg)	x (xx, xx)	x (xx, xx)	x (xx, xx)	x (xx, xx)	x (xx, xx)	x (xx, xx)
Ae ₆₀₋₇₂ (mg)	x (xx, xx)	x (xx, xx)	x (xx, xx)	x (xx, xx)	x (xx, xx)	x (xx, xx)

Note: Values of Mean (Min, Max) are shown, except for CL_R, for which values of GM (CV %) are shown.

^a Times are relative to time of dosing.

Table 88: Summary Statistics for VT-1598 PK Parameters in Urine, 40 mg Fasted Dose Group

Statistics	Inpatient Period (0-72 h) ^a			Nominal Collection Time Interval ^a						
	A _e _{last} (mg)	A _e %Dose (%)	CLR (mL/min)	A _e 0-6 (mg)	A _e 6-12 (mg)	A _e 12-24 (mg)	A _e 24-36 (mg)	A _e 36-48 (mg)	A _e 48-60 (mg)	A _e 60-72 (mg)
N	X	X	X	X	X	X	X	X	X	X
Mean	X	X	X	X	X	X	X	X	X	X
SD	X	X	X	X	X	X	X	X	X	X
Min	X	X	X	X	X	X	X	X	X	X
Max	X	X	X	X	X	X	X	X	X	X
CV %	X	X	X	X	X	X	X	X	X	X
GM	X	X	X	X	X	X	X	X	X	X

^a Times are relative to time of dosing.

Table 89: Summary Statistics for VT-1598 PK Parameters in Urine, 80 mg Fasted Dose Group

This table will repeat Table 88 for VT-1598 PK parameters in Urine for the 80 mg Fasted Dose Group

Table 90: Summary Statistics for VT-1598 PK Parameters in Urine, 160 mg Fasted Dose Group

This table will repeat Table 88 for VT-1598 PK parameters in Urine for the 160 mg Fasted Dose Group

Table 91: Summary Statistics for VT-1598 PK Parameters in Urine, 160 mg Fed Dose Group

This table will repeat Table 88 for VT-1598 PK parameters in Urine for the 160 mg Fed Dose Group

Table 92: Summary Statistics for VT-1598 PK Parameters in Urine, 320 mg Fasted Dose Group

This table will repeat Table 88 for VT-1598 PK parameters in Urine for the 320 mg Fasted Dose Group

Table 93: Summary Statistics for VT-1598 PK Parameters in Urine, 640 mg Fasted Dose Group

This table will repeat Table 88 for VT-1598 PK parameters in Urine for the 640 mg Fasted Dose Group

Table 94: Summary Statistics for VT-11134 PK Parameters in Urine by Dose Group

	40 mg Fasted	80 mg Fasted	160 mg Fasted	160 mg Fed	320 mg Fasted	640 mg Fasted
Inpatient Period (0-72 h)^a						
Ae _{last} (mg)	x (xx, xx)	x (xx, xx)	x (xx, xx)	x (xx, xx)	x (xx, xx)	x (xx, xx)
CL _R (mL/min)	x (x)	x (x)	x (x)	x (x)	x (x)	x (x)
Nominal Collection Time Interval^a						
Ae ₀₋₆ (mg)	x (xx, xx)	x (xx, xx)	x (xx, xx)	x (xx, xx)	x (xx, xx)	x (xx, xx)
Ae ₆₋₁₂ (mg)	x (xx, xx)	x (xx, xx)	x (xx, xx)	x (xx, xx)	x (xx, xx)	x (xx, xx)
Ae ₁₂₋₂₄ (mg)	x (xx, xx)	x (xx, xx)	x (xx, xx)	x (xx, xx)	x (xx, xx)	x (xx, xx)
Ae ₂₄₋₃₆ (mg)	x (xx, xx)	x (xx, xx)	x (xx, xx)	x (xx, xx)	x (xx, xx)	x (xx, xx)
Ae ₃₆₋₄₈ (mg)	x (xx, xx)	x (xx, xx)	x (xx, xx)	x (xx, xx)	x (xx, xx)	x (xx, xx)
Ae ₄₈₋₆₀ (mg)	x (xx, xx)	x (xx, xx)	x (xx, xx)	x (xx, xx)	x (xx, xx)	x (xx, xx)
Ae ₆₀₋₇₂ (mg)	x (xx, xx)	x (xx, xx)	x (xx, xx)	x (xx, xx)	x (xx, xx)	x (xx, xx)

Note: Values of Mean (Min, Max) are shown, except for CL_R for which values of GM (CV %) are shown.^a Times are relative to time of dosing.

Table 95: Summary Statistics for VT-11134 PK Parameters in Urine, 40 mg Fasted Dose Group

Statistics	Inpatient Period (0-72 h) ^a		Nominal Collection Time Interval ^a							
	A _e _{last} (mg)	CL _R (mL/min)	A _e ₀₋₆ (mg)	A _e ₆₋₁₂ (mg)	A _e ₁₂₋₂₄ (mg)	A _e ₂₄₋₃₆ (mg)	A _e ₃₆₋₄₈ (mg)	A _e ₄₈₋₆₀ (mg)	A _e ₆₀₋₇₂ (mg)	
N	x	x	x	x	x	x	x	x	x	
Mean	x	x	x	x	x	x	x	x	x	
SD	x	x	x	x	x	x	x	x	x	
Min	x	x	x	x	x	x	x	x	x	
Max	x	x	x	x	x	x	x	x	x	
CV %	x	x	x	x	x	x	x	x	x	
GM	x	x	x	x	x	x	x	x	x	

^a Times are relative to time of dosing.

Table 96: Summary Statistics for VT-11134 PK Parameters in Urine, 80 mg Fasted Dose Group

This table will repeat Table 95 for VT-11134 PK parameters in Urine for the 80 mg Fasted Dose Group

Table 97: Summary Statistics for VT-11134 PK Parameters in Urine, 160 mg Fasted Dose Group

This table will repeat Table 95 for VT-11134 PK parameters in Urine for the 160 mg Fasted Dose Group

Table 98: Summary Statistics for VT-11134 PK Parameters in Urine, 160 mg Fed Dose Group

This table will repeat Table 95 for VT-11134 PK parameters in Urine for the 160 mg Fed Dose Group

Table 99: Summary Statistics for VT-11134 PK Parameters in Urine, 320 mg Fasted Dose Group

This table will repeat Table 95 for VT-11134 PK parameters in Urine for the 320 mg Fasted Dose Group

Table 100: Summary Statistics for VT-11134 PK Parameters in Urine, 640 mg Fasted Dose Group

This table will repeat Table 95 for VT-11134 PK parameters in Urine for the 640 mg Fasted Dose Group

Table 101: Assessment of Dose Proportionality Among Fasted Dose Groups

Statistic	VT-1598			VT-11134		
	C _{max}	AUC _{0-last}	AUC _{0-inf}	C _{max}	AUC _{0-last}	AUC _{0-inf}
	(ng/mL)	(ng*h/mL)	(ng*h/mL)	(ng/mL)	(ng*h/mL)	(ng*h/mL)
Lowest Dose Included (mg)	x	x	x	x	x	x
Highest Dose Included (mg)	x	x	x	x	x	x
ρ	x	x	x	x	x	x
β -hat	x.XXX	x.XXX	x.XXX	x.XXX	x.XXX	x.XXX
Standard Error (β -hat)	x.XXX	x.XXX	x.XXX	x.XXX	x.XXX	x.XXX
$\rho^{\beta\text{-hat}-1}$ 90% CI	(x.xx, x.xx)	(x.xx, x.xx)	(x.xx, x.xx)	(x.xx, x.xx)	(x.xx, x.xx)	(x.xx, x.xx)
Conclude parameter shows dose proportionality?	Yes/No	Yes/No	Yes/No	Yes/No	Yes/No	Yes/No

Note: β -hat is an estimate obtained using the linear model $\log(\text{Param}) = \alpha + \text{dose} \times \beta$, where Param is AUC_{0-last}, AUC_{0-inf}, or C_{max}. Perfect dose proportionality is equivalent to $\beta = 1$. The value ρ is equivalent to the ratio of the highest dose included in the analysis divided by the lowest dose included in the analysis. Presence of dose proportionality is concluded when the 90% confidence interval for $\rho^{\beta\text{-hat}-1}$ is contained within the interval (0.80,1.25).

Table 102: Comparison of T_{max} between Fasted and Fed 160 mg Dose Groups

[Implementation Note: Since fewer than 3 subjects in the PK Analysis Population were in both Cohort 3 and Cohort 6 then the Wilcoxon signed-rank test comparing T_{max} (Paired) between the cohorts will not be conducted. The N, Estimate, and 90% CI cells should be “-“ and a footnote should be added to explain why they are missing.]

Parameter	Estimand	Subjects Included	VT-1598			VT-11134		
			N ^a	Estimate	90% CI ^b	N ^a	Estimate	90% CI ^b
T _{max} (Paired)	Median of (160 mg Fed T _{max}) - (160 mg Fasted T _{max})	Subjects who received 160 mg of VT-1598 in both Cohort 3 (Fast) and Cohort 6 (Fed).	x	x	(x, x)	x	x	(x, x)
T _{max} (Independent)	(160 mg Fed T _{max} Median) - (160 mg Fasted T _{max} Median)	Any subject who received 160 mg of VT-1598 in either Cohort 3 (Fast) or Cohort 6 (Fed)	x	x	(x, x)	x	x	(x, x)

^a N=Number of subjects with data used to compute T_{max}. In the paired comparison, data was used from any subject in the PK Analysis Subset who received 160 mg VT-1598 under both a fasted and fed state. In the independent comparison, data was used from any subject in the PK Analysis Subset who received 160 mg VT-1598 under either a fasted or fed state, regardless of whether or not the subject participated in both study parts.

^b The 90% CI for subjects who receive VT-1598 and participated in both cohorts was calculated using Wilcoxon signed-rank test. The 90% CI for all subjects who received VT-1598 in either cohort was calculated using a Wilcoxon rank sum test.

Table 103: Comparison of Plasma PK Exposure Parameters between Fasted and Fed 160 mg Dose Groups – VT-1598

Exposure Parameter Comparison	VT-1598			VT-11134		
	N ^a	Estimate	90% CI ^b	N ^a	Estimate	90% CI ^b
C _{max} Ratio (Fed/Fast)	x	x	(x, x)	x	x	(x, x)
AUC _(0-last) Ratio (Fed/Fast)	x	x	(x, x)	x	x	(x, x)
AUC _(0-inf) Ratio (Fed/Fast)	x	x	(x, x)	x	x	(x, x)

^aN=Number of subjects with data used to compute the exposure parameters. Data was used from any subject in the PK Analysis Subset who received 160 mg VT-1598 under either a fasted or fed state, regardless of whether or not the subject participated in both study parts. BQL values were imputed as 0 if the sample was taken before the first measurable PK sample with a concentration above the LLOQ. BQL values were treated as missing otherwise.

^b90% CI estimated using a mixed effects model for the geometric mean of each parameter by fasting status with a random subject effect. Individual parameter estimates were log transformed before inclusion in the model.

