### 10.5.2 Clinical Safety Labs, Vital Signs, and Electrocardiograms

Baseline for clinical safety labs, vital signs, and ECGs will be defined as the last result obtained before the dose of study product. Clinical safety labs, vital signs, and ECGs results and changes from baseline will be summarized by treatment arm and visit. Clinical safety labs and vital signs will be graded ([Appendix B](#)) and summarized by severity, treatment arm, and visit. If triplicate ECG measurements were performed at the same visit, then baseline is the mean value of the measurements for the visit closest to, but before, administration of study drug. Similarly, for analyses of change from baseline, mean values will be used in the case of replicate measurements at a single visit post-baseline.

Treatment-emergent abnormal laboratory test results will be identified. Treatment-emergent abnormal laboratory tests are tests for which the result was not graded as mild or worse at baseline but graded as mild or worse after dosing. Laboratory tests graded as mild at baseline,

but moderate or worse any time after dosing will also be regarded as treatment-emergent abnormal laboratory test results.

ECG measurements will include heart rate, RR interval, QT interval, QTcF interval, PR interval, and QRS duration. Baseline for ECG measurements is defined per protocol as the value pre-dosing on Day 1. Change from baseline will be summarized descriptively by regimen at each scheduled evaluation. QTc results will be summarized categorically according to the ICH Guideline E14 “Clinical Evaluation of QT/QTc Interval Prolongation and Proarrhythmic Potential for Non-Antiarrhythmic Drugs” (October 2005).

- QTcF >450 ms;
- QTcF >450 ms, males only;
- QTcF >470 ms, females only;
- QTcF >480 ms;
- QTcF >500 ms;
- QTcF increases from baseline by at least 30 ms but less than 60 ms;
- QTcF increases from baseline by at least 60 ms.

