7. Males* having sexual intercourse with women of childbearing potential must agree to consistent use of condoms from study product administration through 3 months after dosing**;

** Including vasectomized men.*

*** And must also agree to not donate sperm during this same time period.*

8. Subject has adequate venous access for blood collection.

Exclusion Criteria:

1. Has a chronic condition that may increase risk to subject or interfere with endpoint assessment (e.g., liver disease, kidney disease, immunodeficiency);

2. Chronic condition diagnosed within 90 days of the Screening visit;

3. Unstable chronic disease* within 6 months of the Screening visit;

**As defined by need for medical intervention that lead to a change in medications and/or required hospitalization, surgery/procedure, or Emergency Department/urgent care visit.*

4. History of psychiatric condition that has required hospitalization in the last 5 years or patient is considered unstable by study investigator;

5. Any condition that is in the opinion of the Investigator could significantly impact drug absorption, distribution, or elimination;

6. Any out of normal range value* at Screening or enrollment (Section 8.1 and Appendix B of the protocol);

**A laboratory value that is Grade 1 (with the exception of alanine aminotransferase (ALT), aspartate aminotransferase (AST), Total bilirubin, hemoglobin or serum creatinine) will be allowed if not considered to be clinically significant by the investigator.*

7. Abnormal ECGs. See Section 7.1 of the protocol Clinical Evaluations for exceptions;

8. Electrocardiographic QTcF interval >430 msec for males and >450 msec for females at Screening;

9. Positive test for antibodies to Human Immunodeficiency Virus (HIV)-1, HIV-2, Hepatitis B Surface Antigen (HBsAg), or Hepatitis C Virus (HCV);

10. Positive urine drug test. The drugs that will be screened for includes amphetamines, barbiturates, cocaine, opiates, cannabinoids, phencyclidine, and benzodiazepines;

11. Female subject of childbearing potential who is pregnant*, lactating, or planning to become pregnant during the study period or 3 months after the final dose of study product;

**Having a positive serum pregnancy test at the Screening Visit or any other specified timepoint prior to the dose of the study product.*

12. Received any study product in a clinical trial within 30 days prior to Screening;

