TOXICITYGRADING CRITERIA FOR NORMAL HUMAN SUBJECTS, will be evaluated by the study clinicians, recorded in the source document and, if clinically significant, considered AEs and graded according to the criterion described in version 5.0 of the study Protocol Section 8.1.

° Hematuria during active menses is considered not clinically significant.

Table 5: Vital Signs Toxicity Grading Scale

Parameter	Direction	Mild (Grade 1)	Moderate (Grade 2)	Severe (Grade 3)
Fever (°C)	Increase	38.0-38.4	38.5-38.9	39.0-40
Fever (°F)	Increase	100.4-101.1	101.2-102.0	102.1-104
Tachycardia (bpm)	Increase	101-115	116-130	>130
Bradycardia (bpm), if baseline > 60	Decrease	50-54	45-49	<45
Bradycardia (bpm), if baseline ≤ 60	Decrease	45-50	40-44	<40
Hypertension (systolic) (mmHg)	Increase	141-150	151-155	>155
Hypotension (systolic) (mmHg)	Decrease	85-89	80-84	<80
Hypertension (diastolic) (mmHg)	Increase	91-95	96-100	>100
Respiratory Rate (breaths/minute)	Increase	17-20	21-25	>25

Table 6: ECG Toxicity Grading Scale

Parameter	Direction	Mild (Grade 1)	Moderate (Grade 2)	Severe (Grade 3)
QTcF (ms)	Increase	> 30 but \leq 60 above baseline	> 60 above baseline to \leq 500	>500

Table 7: Analysis Timepoints for Safety and PK Endpoints

Parameter	Analysis Timepoint	Abbreviated Label	Endpoint
CHEM, HEM, COAG, UA VS ECG	Screening	N/A	CHEM, HEM, COAG, UA, VS, ECG
	Admission (Baseline)/ Admission	d-1	CHEM, HEM, COAG, UA/ VS, ECG
	Day 1, Pre-Dose (Baseline)	0 h	VS, ECG
	Maximum Severity Post baseline	N/A	CHEM, HEM, COAG, UA, VS, ECG
	Day 1, 1 h Post Dose	1 h	VS
	Day 1, 2 h Post Dose	2 h	VS
	Day 1, 4 h Post Dose	4 h	VS
	Day 1, 8 h Post Dose	8 h	VS
	Day 2	d2	VS
	Day 3	d3	VS
	Day 4	d4	CHEM, HEM, COAG, UA, VS, ECG
	Day 7	d7	CHEM, HEM, COAG, UA, VS
	Day 14	d14	CHEM, HEM, COAG, UA, VS
	Day 21	d21	CHEM, HEM, COAG, UA, VS, ECG
PK	Day 1, Pre-Dose	0 h	Plasma
	Day 1, Pre-Dose	-6-0 h	Urine
	Day 1, 0.5 h Post Dose	0.5 h	Plasma
	Day 1, 1 h Post Dose	1 h	Plasma
	Day 1, 1.5 h Post Dose	1.5 h	Plasma
	Day 1, 2 h Post Dose	2 h	Plasma
	Day 1, 3 h Post Dose	3 h	Plasma
	Day 1, 4 h Post Dose	4 h	Plasma
	Day 1, 6 h Post Dose	6 h	Plasma
	Day 1, 0-6 h Post Dose	0-6 h	Urine
	Day 1, 8 h Post Dose	8 h	Plasma
	Day 1, 10 h Post Dose	10 h	Plasma
	Day 1, 12 h Post Dose	12 h	Plasma
	Day 1, 6-12 h Post Dose	6-12 h	Urine
	Day 1, 14 h Post Dose	14 h	Plasma
	Day 2, 24 h Post Dose	24 h	Plasma
	Day 1, 12-24 h Post Dose	12-24 h	Urine
	Day 2, 36 h Post Dose	36 h	Plasma
	Day 2, 24-36 h Post Dose	24-36 h	Urine

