QTcF Category	Timepoint	N	Any Dose	40 mg Fasted	80 mg Fasted	160 mg Fasted	160 mg Fed	320 mg Fasted	640 mg Fasted	Placebo
			n (%)	n (%)	n (%)	n (%)	n (%)	n (%)	n (%)	n (%)
QTcF >450 ms, Male	Day 1, 4 h Post-Dose	x	x (xx)	x (xx)	x (xx)	x (xx)	x (xx)	x (xx)	x (xx)	x (xx)
		x	x (xx)	x (xx)	x (xx)	x (xx)	x (xx)	x (xx)	x (xx)	x (xx)
		x	x (xx)	x (xx)	x (xx)	x (xx)	x (xx)	x (xx)	x (xx)	x (xx)
	Day 7	x	x (xx)	x (xx)	x (xx)	x (xx)	x (xx)	x (xx)	x (xx)	x (xx)
		x	x (xx)	x (xx)	x (xx)	x (xx)	x (xx)	x (xx)	x (xx)	x (xx)
		x	x (xx)	x (xx)	x (xx)	x (xx)	x (xx)	x (xx)	x (xx)	x (xx)
	Day 21	x	x (xx)	x (xx)	x (xx)	x (xx)	x (xx)	x (xx)	x (xx)	x (xx)
		x	x (xx)	x (xx)	x (xx)	x (xx)	x (xx)	x (xx)	x (xx)	x (xx)
		x	x (xx)	x (xx)	x (xx)	x (xx)	x (xx)	x (xx)	x (xx)	x (xx)
QTcF >470 ms, Female	Day 1, 4 h Post-Dose	x	x (xx)	x (xx)	x (xx)	x (xx)	x (xx)	x (xx)	x (xx)	x (xx)
	...	x	x (xx)	x (xx)	x (xx)	x (xx)	x (xx)	x (xx)	x (xx)	x (xx)
QTcF >480 ms	Day 1, 4 h Post-Dose	x	x (xx)	x (xx)	x (xx)	x (xx)	x (xx)	x (xx)	x (xx)	x (xx)
	...	x	x (xx)	x (xx)	x (xx)	x (xx)	x (xx)	x (xx)	x (xx)	x (xx)
QTcF >500 ms	Day 1, 4 h Post-Dose	x	x (xx)	x (xx)	x (xx)	x (xx)	x (xx)	x (xx)	x (xx)	x (xx)
	...	x	x (xx)	x (xx)	x (xx)	x (xx)	x (xx)	x (xx)	x (xx)	x (xx)
30 ms ≤ QTcF increases from baseline < 60 ms	Day 1, 4 h Post-Dose	x	x (xx)	x (xx)	x (xx)	x (xx)	x (xx)	x (xx)	x (xx)	x (xx)
	...	x	x (xx)	x (xx)	x (xx)	x (xx)	x (xx)	x (xx)	x (xx)	x (xx)
QTcF increases from baseline ≥ 60 ms	Day 1, 4 h Post-Dose	x	x (xx)	x (xx)	x (xx)	x (xx)	x (xx)	x (xx)	x (xx)	x (xx)
	...	x	x (xx)	x (xx)	x (xx)	x (xx)	x (xx)	x (xx)	x (xx)	x (xx)

Note: N=Number of subjects in Safety Population with the ECG results assessed at the respective timepoint. N is calculated based on specified sex for “QTcF >450 ms, Male” and “QTcF >470 ms, Female” categories.

Table 45: VT-1598 Concentrations in Plasma by Dose Group – 0 h to 14 h Post Dose

Dose Group	Nominal Time ^a (h)										
	0	0.5	1.5	2	3	4	6	8	10	12	14
40 mg Fasted	x (x)	x (x)	x (x)	x (x)	x (x)	x (x)	x (x)	x (x)	x (x)	x (x)	x (x)
80 mg Fasted	x (x)	x (x)	x (x)	x (x)	x (x)	x (x)	x (x)	x (x)	x (x)	x (x)	x (x)
160 mg Fasted	x (x)	x (x)	x (x)	x (x)	x (x)	x (x)	x (x)	x (x)	x (x)	x (x)	x (x)
160 mg Fed	x (x)	x (x)	x (x)	x (x)	x (x)	x (x)	x (x)	x (x)	x (x)	x (x)	x (x)
320 mg Fasted	x (x)	x (x)	x (x)	x (x)	x (x)	x (x)	x (x)	x (x)	x (x)	x (x)	x (x)
640 mg Fasted	x (x)	x (x)	x (x)	x (x)	x (x)	x (x)	x (x)	x (x)	x (x)	x (x)	x (x)

Notes: Concentrations are reported in units of ng/mL.

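### SAP Table 44 omits the protocol's all-subject QTcF >450 ms category without saying so, leaving women at 451-470 ms in no absolute QTcF category

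*SAP*

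**What the plan says.** Protocol 10.5.2 states that "QTc results will be summarized categorically according to the ICH Guideline E14" and gives seven categories. Five are absolute: >450 ms with no sex restriction, then "QTcF >450 ms, males only", "QTcF >470 ms, females only", >480 ms and >500 ms. Two are changes from baseline: 30 to under 60 ms, and 60 ms or more.

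SAP 9.8 lists no categories and refers the categorical summary to Table 44, so that shell is the specification. Table 44 opens with "QTcF >450 ms, Male", continues with "QTcF >470 ms, Female", >480 ms and >500 ms, and ends with the same two change categories. Its note says "N is calculated based on specified sex for “QTcF >450 ms, Male” and “QTcF >470 ms, Female” categories", so the >450 ms row has a male-only denominator.

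The other graded QTcF summary is Table 42, which uses the scale in SAP Table 6. Grade 1 is a rise above 30 and up to 60 ms, Grade 2 is "> 60 above baseline to" 500 ms, and Grade 3 is above 500 ms.

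SAP 4.3 (exclusion 8) excludes "Electrocardiographic QTcF interval >430 msec for males and >450 msec for females at Screening", so a woman with a screening QTcF of up to 450 ms can enrol.

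Protocol Section 10 requires departures from its analyses to be described in the SAP. SAP Section 15 describes one, the Tmax comparison after only one Cohort 3 subject returned for Cohort 6.

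**The concern.** For men the dropped category duplicates the male >450 ms row, so nothing is lost. For women it was the only absolute category between 450 and 470 ms. Because women may enter with a QTcF up to 450 ms, it was also the first absolute level that a woman could newly cross after dosing.

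ECG results are part of the primary safety outcome. The protocol reports a mild QTc increase in monkeys at the top dose of the 28-day study and lists QT prolongation among the risks of some other azoles. With six active subjects per dose group, one woman more or less in a category is visible in the table. A protocol-specified primary-safety summary would therefore be reported with one sex's lower band missing, and a reader of the SAP alone would not know that a category had been removed.

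**Working it through.** **1. The two lists side by side**

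| Category | Protocol 10.5.2 | SAP Table 44 |
|---|---|---|
| >450 ms, all subjects | yes | **no** |
| >450 ms, males | yes | yes |
| >470 ms, females | yes | yes |
| >480 ms | yes | yes |
| >500 ms | yes | yes |
| rise 30 to <60 ms | yes | yes |
| rise ≥60 ms | yes | yes |
| Total | 7 | 6 |

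**2. Which values lose their absolute category**

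Every integer QTcF from 451 to 510 ms was classified by sex under both lists.

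- Protocol list: no uncovered value in either sex.
- Table 44: no uncovered value in men. In women, 451 to 470 ms is uncovered, which is 470 − 451 + 1 = 20 integer values.
- Table 44 with the all-subject row restored: no uncovered value in either sex.

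**3. Worked examples, women**

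| Baseline → post-dose (ms) | Change (ms) | Protocol categories | Table 44 categories | Table 42 grade |
|---|---|---|---|---|
| 435 → 460 | +25 | >450 all | none | none |
| 445 → 470 | +25 | >450 all | none | none |
| 430 → 459 | +29 | >450 all | none | none |
| 430 → 460 | +30 | >450 all; 30 to <60 | 30 to <60 | none |
| 415 → 455 | +40 | >450 all; 30 to <60 | 30 to <60 | Mild |
| 405 → 466 | +61 | >450 all; ≥60 | ≥60 | Moderate |
| 450 → 471 | +21 | >450 all; >470 F | >470 F | none |

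So a woman at 451-470 ms is in no absolute category whatever her change. With a rise under 30 ms she is in no Table 44 category and has no Table 42 grade.

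**4. How often this could happen**

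The documents give no QTcF distribution and no human drug effect, so every input except the 450 ms screening limit is an assumption: women's true QTcF T ~ N(m, 15) with m = 405, 415 or 420 ms, reading SD 6, and drug effect d. A woman is kept if T + e1 ≤ 450 at screening. Baseline is B = T + e2 and the post-dose value is Q = T + d + e3. The band is 450 < Q ≤ 470 and the change is Q − B.

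Simulated percentages of women at one visit, for m = 405 / 415 / 420:

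| d (ms) | In 451-470 band | Above 470 ms | In band with rise <30 ms |
|---|---|---|---|
| 0 | 0.2 / 0.8 / 1.5 | 0.0 / 0.0 / 0.0 | 0.2 / 0.8 / 1.5 |
| 10 | 1.3 / 4.8 / 8.1 | 0.0 / 0.1 / 0.1 | 1.2 / 4.6 / 7.9 |
| 20 | 5.7 / 15.6 / 22.9 | 0.2 / 0.8 / 1.5 | 4.3 / 12.4 / 18.6 |

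Hand check at m = 415, d = 20, ignoring the screening truncation: SD of Q = √(15² + 6²) = 16.16, and Φ((470 − 435)/16.16) − Φ((450 − 435)/16.16) = Φ(2.17) − Φ(0.93) ≈ 0.985 − 0.823 = 16%. This agrees with 15.6% after truncation.

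At d = 30 the change rows catch most of the band: 56%-65% of women in it have a rise of at least 30 ms.

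In head counts, if three of six active subjects in a group are women (also an assumption), +10 ms gives 3 × 0.013 = 0.04 to 3 × 0.081 = 0.24 women in the band per group and visit, and +20 ms gives 3 × 0.057 = 0.17 to 3 × 0.229 = 0.69.

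**The case against.** The strongest reply is that the protocol itself sets a separate female threshold of 470 ms and the SAP keeps it. On that threshold a woman at 451-470 ms is not an outlier, so each sex is counted at its own limit and the all-subject row adds little. This has weight: the omission should not be read as a demonstrated bias against detecting an effect in women. It does not explain the departure, because the protocol lists the all-subject category in addition to the sex-specific ones and the SAP gives no reason for removing it.

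A reader might infer that these women vanish from the report. They do not. Listing 21 gives every QTcF value with sex and change from baseline, Table 43 and Figure 62 include their changes, and Table 41 counts a shift from normal to abnormal if the reader calls the ECG abnormal. That last route depends on a clinical judgement, not on a QTcF threshold, and none of these replaces a count above 450 ms.

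A reader might also infer a risk to subjects or to escalation. The cohort halting rule in Protocol 8.6.2 uses QTcF above 500 ms or a rise above 60 ms, so no halting decision rests on 450 ms.

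The frequencies depend on the assumed effect, and the nonclinical evidence is mixed. The monkey QTc increase was mild and occurred at a dose still called the NOAEL. Telemetered monkeys showed no adverse QT/QTc change at up to 300 mg/kg twice daily for 7 days, and there was no hERG inhibition up to the highest soluble concentration tested. The documents do not support a particular effect such as +20 ms.

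Finally, the first block of Table 44 is broken in the extracted text, so a lost row cannot be excluded outright. It is unlikely, since the other six categories and the note on sex-specific denominators are intact, though that note would read the same with an all-subject row present.

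**Conclusion.** The point holds as a discrepancy between protocol and SAP with a definite consequence. One of seven protocol categories is missing from the only table with absolute QTcF thresholds below 500 ms, and the departure is not declared. Women at 451-470 ms are then in no absolute category, and those with a rise under 30 ms are in no Table 44 category and no Table 42 grade. That much follows from the two lists and needs no assumption.

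The number affected is uncertain. On the assumed means (405-420 ms) and SDs (15 between women, 6 per reading), about 0.2%-1.5% of women per visit fall in the band with no drug effect, 1%-8% at +10 ms and 6%-23% at +20 ms. These are illustrations, not predictions for VT-1598.

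The harm is confined to descriptive safety reporting. It should be corrected because the summary is specified in the protocol and belongs to the primary safety outcome; it does not put the conduct of the trial in question.

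**What to change.** Add a row block for QTcF >450 ms in all subjects to SAP Table 44, at the same timepoints as the other categories, with N equal to all subjects in the Safety Population assessed at that timepoint. Keep the male >450 ms and female >470 ms rows with their sex-specific N. The cost is one row block in one table shell and its program; no new data are needed.

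If the sponsor means to leave the category out, SAP Section 15 should say so and give the reason, as Protocol Section 10 requires. That would settle the undeclared departure but would leave the 451-470 ms gap for women.
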